7.2. Restrictions During the Study

The following restrictions apply for the specified times during the study period:

- 1 Prior to Day 1 in each treatment period, all subjects will fast for 10 hours overnight before the morning dose procedures. No fluids will be allowed apart from water which can be given until 1 hour before verinurad administration and then from 1 hour after verinurad administration, beverages provided with the high-fat breakfast in periods with dosing under fed conditions and water given during administration. Verinurad will be administered with 240 mL of water on Day 1 of each treatment period under either fasted or fed conditions. All subjects will be instructed to drink approximately 2 L to 2.5 L of liquid a day (including Day -1) during the entire study. During fed dosing, subjects will be provided with a Food and Drug Administration (FDA) high-fat, high-calorie breakfast 30 minutes before the scheduled dosing time (following the overnight fast as above), subjects should consume the breakfast within 25 minutes and finish the breakfast approximately 5 min before the scheduled dosing. During the fasted dosing, subjects will remain fasted for dosing. For both dosing states, no food will be allowed for at least 4 hours after dosing.
- 2 Subjects should not engage in any strenuous activity from 72 hours prior to check-in (Day -1 of Treatment Period 1) until after their Follow-up Visit.
- 3 Subjects should abstain from alcohol for the duration of the study from the first check-in (Day -1 of Treatment Period 1) until after their last PK sampling visit. Subjects should also abstain from alcohol for 72 hours before the Screening Visit and their Follow-up Visit.
- 4 Subjects should abstain from caffeine-containing foods and beverages for 24 hours prior to first check-in (Day -1 of Treatment Period 1) until the Follow-up Visit.
- 5 Subjects should abstain from grapefruit or grapefruit juice, Seville oranges, quinine (e.g., tonic water) from 7 days prior to check-in (Day -1 of Treatment Period 1) until after their Follow-up Visit.
- 6 During admission periods, subjects will receive a standard diet, which excludes all alcohol and grapefruit-containing products. No additional food or beverages must be consumed while in the Clinical Unit.
- 7 During the subjects' outpatient periods, subjects should abstain from consuming, high-energy drinks (e.g., red bull), and food containing poppy seeds and any Over-the-Counter (OTC) medication or herbal preparations until after their Follow-up Visit has been completed.

- 8 Subjects will be required to abstain from blood or plasma donation until 3 months after the final medical examination at the study follow-up.

For medication restrictions, refer to Section 9.7.

7.2.1. Reproductive Restrictions

7.2.1.1. Female Subjects

A female subject who participates in the clinical trial must either:

- Be of non-childbearing potential (surgically sterilized or postmenopausal as described in Section 7.2.1.1.1, OR
- Of child-bearing potential and must be using highly effective methods of birth control as described in Section 7.2.1.1.2.

7.2.1.1.1. Women of Non-Child Bearing Potential

Women of non-childbearing potential are defined as female subjects who are permanently surgically sterilized or postmenopausal.

Acceptable methods of sterilization include:

- Surgical bilateral oophorectomy (with or without hysterectomy) at least six weeks before Screening. In the case of oophorectomy alone, only when the reproductive status of the woman has been confirmed by follow-up hormone level assessment.
- Hysterectomy at least six weeks before Screening.
- Bilateral salpingectomy.

Females are considered postmenopausal if they have had amenorrhea for at least 12 months or more following cessation of all exogenous hormonal treatments and FSH levels are in the postmenopausal range (e.g., age appropriate, history of vasomotor symptoms) or for women < 60 years the FSH levels is > 40 mIU/mL.)

7.2.1.1.2. Women of Child Bearing Potential

Women of child bearing potential who are sexually active must agree to use, with their partner, an approved method of highly effective contraception from the time of verinurad administration until 3 months after the study Follow-up Visit.

- A barrier method must be used in combination with one of the following methods, considered to be highly effective (failure rate < 1% per year when used consistently and correctly):
 - hormonal contraception, i.e., combined oral contraceptives, injectable¹ or implantable¹ hormonal contraceptives,

- hormonal or non-hormonal intrauterine device¹ (IUD, loop), established IUD¹ or intrauterine system (Note: The IUD must have a failure rate < 1%),
- Surgical sterilization¹ (i.e., bilateral tubal ligation for females; vasectomy for male partners [must have been vasectomized before the female subject entered the clinical trial and he is the sole sexual partner of the female subject during the clinical trial,])
- observe abstinence (acceptable only if it is the subject's usual lifestyle).
- Barrier methods of contraception include:
 - Condom (**without** spermicidal foam/gel/film/cream/suppository or fat- or oil-containing lubricants),
 - Occlusive cap (diaphragm or cervical/vault caps) **with** spermicidal gel/film/cream/suppository,
- ¹ These methods are considered to have low user dependency.

Note: Double-barrier is not considered a highly effective method.

Female subjects must agree not to attempt to become pregnant, must not donate ova and must not breastfeed starting at screening and throughout the clinical study and for 90 days (3 months) after the Follow-up Visit.

Women should be informed of the potential risks associated with becoming pregnant while enrolled.

Alternatively, * true abstinence is acceptable when it is in line with the subject's preferred and usual lifestyle.

**True abstinence: When this is in line with the preferred and usual lifestyle of the subject. (Periodic abstinence [e.g., calendar, ovulation, symptothermal, post-ovulation methods], declaration of abstinence for the duration of a trial and withdrawal are not acceptable methods of contraception).*

Pregnancy Testing

Women of child-bearing potential can be included only after a negative highly sensitive serum pregnancy test. Additionally, urine pregnancy testing will be done as per the Schedule of Assessments (Table 5-2).

7.2.1.2. Male Subjects

Restrictions for male subjects

Verinurad had no effects on fertility or embryo-foetal development in rats at doses up to 300 mg/kg/day and did not affect embryo-foetal development in rabbits at doses up to 30 mg/kg/day.

Male subjects participating in this study are not required to apply contraception. However, it is recommended that male subjects should not donate sperm until at least 3 months after the Follow-up Visit. In addition, as a precaution, all male subjects should avoid fathering a child AND exposing a foetus to verinurad by either true abstinence or use together, with their female partner/spouse, of a highly effective method of contraception (see definition above), starting from the time of verinurad administration until at least 3 months after the Follow-up Visit.

Pregnancy

Subjects will be instructed that if their partner becomes pregnant during the study this should be reported to the PI. The PI should also be notified of pregnancy occurring during the study but confirmed after completion of the study. In the event that a subject's partner is subsequently found to be pregnant after the volunteer is included in the study, then consent will be sought from the partner and if granted any pregnancy will be followed and the status of mother and/or child will be reported to the Sponsor after delivery.

A pregnancy notification form and follow-up will be completed.

7.3. Replacement of Subjects

Subjects who are withdrawn from the study due to AEs or changes in safety parameters will not be replaced unless a specific sample size is to be met for statistical purposes and if the Sponsor's responsible physician and the PI agree it is safe to do so. Subjects who withdraw or are withdrawn from the study for other reasons may be replaced following discussion with the Sponsor. Subjects who were screened, but not randomised, may be rescreened as replacement subjects.

Twenty-five (25) subjects will initially be randomised into the study in 5 treatment sequences (5 subjects per treatment sequence) to ensure at least 20 evaluable subjects (4 subjects per treatment sequence) at the end of the study. Subjects will only be replaced if the subject number for evaluable subjects fall below 20 subjects or are less than 4 evaluable subjects per treatment sequence. However, looking at previous studies and previous verinurad experience, at the current study design and dose level, it is highly unlikely to fall below these numbers, and replacements are unlikely to take place.

8. STUDY STOPPING RULES

8.1. Discontinuation of Investigational Medicinal Product and Withdrawal from the Study

Subjects must be discontinued from verinurad in the following situations:

- Subject decision. The subject is at any time free to discontinue treatment, without prejudice to further treatment.
- Severe non-compliance to the Clinical Study Protocol (CSP).
- Any significant and clinically relevant changes in the safety parameters (e.g., ECG, BP, pulse rate, laboratory assessments and AEs) making the continuation of verinurad administration unjustified.
- Study specific withdrawal criteria: If a subject reports symptoms, which are considered unacceptable by the subject or the Investigator, he/she will be withdrawn from the study. In particular:
 - Any other severe or SAE that is judged as possibly related to verinurad by the Investigator.
 - Any case of Potential Hy's Law according to Appendix 16.3.
 - Study treatment will be stopped if a subject has elevated creatinine levels greater than 1.5 times the pre-treatment value and retest of the creatinine will be performed as soon as possible (see Appendix 16.4).
 - In subjects who report symptoms that indicate acute UA nephropathy including flank pain, nausea, or vomiting, treatment will be permanently discontinued. Appendix 16.4 contains guidelines on management of such subjects.
 - See Appendix 16.4 for details on the handling of renal-related or urolithiasis treatment-emergent AEs, and the handling of serum creatinine elevation, which includes criteria for stopping treatment.
 - Pregnancy.
- The appropriate AE form in the case report form is to be completed.

8.2. Premature Termination of the Study and Stopping Criteria

The study will be put on temporary hold (defined as treatment stopped for enrolled subjects; and stop enrolment of subjects into the study) pending further safety data analysis if any of the following criteria occur in subjects receiving verinurad:

- A "serious" adverse reaction (i.e., an SAE considered at least possibly related to verinurad administration as per guideline EMEA/CHMP/SWP/28367/07 Rev. 1) in 1 subject;

- “Severe” non-serious adverse reactions (i.e., severe non-serious AEs considered as, at least, possibly related to the IMP administration) in 2 subjects in the same treatment sequence, independent of within or not within the same System Organ Class (SOC).

The study must be terminated prematurely if:

- The PI and the Sponsor assess that the number and/or severity of AEs justify discontinuation of the study. For instance, when there is at least 1 case of fatal SAE or 2 cases of other SAEs, in both situations considered related to verinurad by the PI and the Sponsor.
- The Sponsor considers the applied doses of the study drug to be no longer relevant.
- The Sponsor decides to discontinue the study.
- Data not known before it become available and raise concern about the safety of verinurad so that continuation would pose potential risks to the subjects.

Premature termination of the study must be mutually agreed upon by the PI and the Sponsor and must be documented. However, study results will be reported according to the requirements outlined in this CSP as far as applicable.

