5.3.2. Overall Study Design

This study will be a randomised, open-label, single-dose, 5-period, 5-treatment, crossover study in healthy male and female subjects, performed at a single study centre.

The study will comprise:

- A screening period of maximum 28 days;
- Five treatment periods during which subjects will be resident from the morning of the day before dosing with verinurad (Day -1) until at least 72 hours after dosing; discharged on the morning of Day 4 of each Treatment Period; and
- A Follow-up Visit within 7 to 14 days after the last administration of verinurad.
- There will be a minimum washout period of 5 days between each dose administration.

A total of 25 healthy male and female subjects will be randomised into this study. Each subject will receive five single-dose treatments of 12 mg verinurad with 240 mL water, following an overnight fast of at least 10 hours:

- Treatment 1: 1 x 12 mg verinurad ER8 capsule formulation, fasted.
- Treatment 2: 2 x 6 mg verinurad A-capsule formulation, fasted.
- Treatment 3: 2 x 6 mg verinurad A-capsule formulation, fed.
- Treatment 4: 2 x 6 mg verinurad B-capsule formulation, fasted.
- Treatment 5: 2 x 6 mg verinurad B-capsule formulation, fed.

For both the fasted and fed dosing, no fluids will be allowed apart from water which can be given until 1 hour prior and 1 hour after administration of verinurad, water to be given with the verinurad administration and beverages provided with the high-fat, high-calorie breakfast (see Section 9.6.1) in dosing periods with the administration under fed conditions. All subjects will be instructed to drink approximately 2 L to 2.5 L of liquid a day (including Day - 1) throughout the duration of the study.

Subjects will follow an overnight fast of at least 10 hours before the dosing procedures: for the fed dosing, a high-fat, high-calorie standard breakfast will be served 30 minutes before the planned administration of verinurad to be consumed in full at least 5 minutes before dosing; for the fasted dosing, no breakfast will be served. A meal can be given 4 hours after administration of verinurad for both dosing states.

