9.9. Randomization

9.9.1. Subject Enrolment and Randomization

The PI will ensure:

- Signed informed consent is obtained from each potential subject before any study specific procedures are performed.
- Each potential subject is assigned a unique enrolment number at screening upon signing the Informed Consent.
- The eligibility of each subject is in accordance with the inclusion and exclusion criteria.
- Each eligible subject is assigned a unique randomization code.

Randomization to be done on Day -1 of Treatment Period 1.

Randomization codes will be assigned strictly sequentially as subjects become eligible for randomization (codes to be used without leading zero[s]).

When using unique enrolment number, the specific format must be followed (i.e., reduced enrolment number “01001” in **CCI** and on labels, full enrolment number “E0001001” for outputs).

If a subject withdraws his/her participation in the study, then his/her enrolment/randomization code cannot be re-used. If a replacement is mandated, replacement subjects will receive a new randomization number and will be allocated to **CCI**

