9.9.2. Procedures for Randomization

Upon completion of the randomization requirements specifications form, the randomization will be produced by PAREXEL according to the AstraZeneca randomization system (AZRand).

Subjects will be randomised to treatment sequences in a ratio of 1:1:1:1:1 so that all subjects will receive all formulations of verinurad. The reference capsules (Treatment 1) will be given under fasted conditions, while the new formulations (Treatments 2, 3, 4 and 5) will be given under both fasted or fed conditions as per study design (see Section 5.3.2).

The randomization will be completed using consecutive randomization codes.

The number of subject identifiers generated for the study will account for the number of randomised subjects per the sample size calculation (N = 20 [see Section 12.4]) as well as providing sufficient randomization numbers for replacements. For this study, a total of

25 subject identifiers will be randomly assigned to the 5 treatment sequences: 12345, 23451, 51234, 34512 and 45123.

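### The hold rule for severe related reactions counts within a randomised sequence, so two severe reactions to the same treatment in different periods never trigger it

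*Protocol*

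**What the plan says.** Section 8.2 lists two events that put the study on temporary hold. It introduces them as applying "if any of the following criteria occur in subjects receiving verinurad". The first is a serious related reaction in one subject, with no reference to sequence. The second is severe non-serious reactions, at least possibly related, and it requires them "in 2 subjects in the same treatment sequence, independent of within or not within the same System Organ Class (SOC").

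The protocol uses the term treatment sequence for the randomised orders. Section 9.9.2: "25 subject identifiers will be randomly assigned to the 5 treatment sequences: 12345, 23451, 51234, 34512 and 45123". Section 7.3: "Twenty-five (25) subjects will initially be randomised into the study in 5 treatment sequences (5 subjects per treatment sequence"). Every order contains every treatment. Section 9.9.2 describes the allocation as made "so that all subjects will receive all formulations of verinurad", and Section 5.3.2 says "Each subject will receive five single-dose treatments of 12 mg verinurad with 240 mL water".

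**The concern.** Counting reactions within a group makes sense when groups differ in dose or product. Here they differ only in the order of the same five treatments, at one dose. Whether the hold fires therefore depends on whether the two affected subjects were randomised to the same order, not on whether they reacted to the same capsule or to verinurad at all.

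Two severe reactions to one new capsule, in different periods, would leave the rule silent while other subjects may still be due that capsule. Two reactions to two different treatments would trigger it if the subjects shared an order. The adverse event analysis in Section 12.10.1 does not use this unit: it summarises by treatment pooled over periods, and overall.

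What is at stake is subject protection. The pharmacokinetic comparisons are not touched.

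**Working it through.** The protocol gives no operating figure for this rule, so there is none to reproduce. The check enumerates the design.

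**Inputs.** Five sequences (Section 9.9.2), 5 subjects each, 25 in total (Section 7.3), threshold of 2 subjects in one sequence (Section 8.2).

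**Step 1: period in which each treatment is given.**

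| Treatment | 12345 | 23451 | 51234 | 34512 | 45123 |
|---|---|---|---|---|---|
| 1 | 1 | 5 | 2 | 4 | 3 |
| 2 | 2 | 1 | 3 | 5 | 4 |
| 3 | 3 | 2 | 4 | 1 | 5 |
| 4 | 4 | 3 | 5 | 2 | 1 |
| 5 | 5 | 4 | 1 | 3 | 2 |

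Each row contains the five periods once. For any treatment, the same sequence means the same period, and different periods mean different sequences.

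**Step 2: pairs of subjects.**
- All pairs: C(25,2) = 300.
- Pairs in the same sequence: 5 × C(5,2) = 50 (16.7%).
- Pairs in different sequences: 300 − 50 = 250 (83.3%).

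For each of the five treatments, 250 pairs receive it in different periods, and none of those 250 shares a sequence.

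**Step 3: more than two affected subjects.** If reactions are unrelated to sequence, the chance that no two of *k* affected subjects share a sequence is C(5,*k*) × 5^*k* / C(25,*k*):
- *k* = 2: 10 × 25 / 300 = 0.833
- *k* = 3: 10 × 125 / 2,300 = 0.543
- *k* = 4: 5 × 625 / 12,650 = 0.247
- *k* = 5: 1 × 3,125 / 53,130 = 0.059

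**Step 4: unconditional chance of a hold.** Let *p* be the chance that a subject has a severe non-serious related reaction, independent between subjects, and *q* = 1 − *p*.
- As written: 1 − (*q*^5 + 5*p* *q*^4)^5
- Counted study-wide: 1 − *q*^25 − 25*p* *q*^24

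| Assumed *p* | As written | Study-wide | Difference (points) |
|---|---|---|---|
| 1/293 | 0.06% | 0.33% | 0.3 |
| 2/293 | 0.23% | 1.26% | 1.0 |
| 2% | 1.91% | 8.86% | 7.0 |
| 5% | 10.80% | 35.76% | 25.0 |

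The first two rates borrow from Section 5.2.3.1, which reports two adverse events above Grade 2 among 293 healthy subjects; they count one or both. That grading scale differs from the one used here, and causality is not stated. The 2% and 5% rates have no source in the protocol and only show the range.

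**Step 5: an example.** Treatment 3 (A-capsule, fed) falls in Period 1 for sequence 34512 and in Period 2 for 23451. One severe related reaction to it in each sequence triggers nothing. If all subjects are dosed in step, the other three sequences, 3 × 5 = 15 subjects, are still due Treatment 3 after Period 2. Dosing in step is an assumption, since Section 9.9.1 says "Randomization codes will be assigned strictly sequentially as subjects become eligible for randomization". Without it, the number still due could be anywhere from 0 (these two subjects enrolled last) to 23 (enrolled first).

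**The case against.** The strongest reply is about weight. At the only rates the protocol can suggest, the rule as written and a study-wide count differ by 0.3 to 1.0 percentage points. Even those rates may be generous: one of the two events was a tooth infection, and the other was a creatinine increase, which has its own stopping rule. This stands, and it limits the severity of the point.

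Other safeguards exist. One related serious event holds the study. Section 8.1 withdraws the affected subject for "Any other severe or SAE that is judged as possibly related to verinurad by the Investigator". Section 8.2 also provides for termination on the number or severity of adverse events, or on new data that raise safety concern. The study is open-label at one centre with residential stays, so events and their treatments will be seen. All true, but these act on other events, on the single affected subject, or by judgement. None supplies the automatic count that the sponsor chose to write in.

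Subjects who share a sequence also share an exposure history, so the rule catches some same-treatment clusters. It does, but only 50 of 300 pairs. The lead-in to the list may likewise be read as a general stem that each criterion can narrow, so this is a poorly chosen unit of counting rather than a strict contradiction.

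Finally, counting study-wide also holds the study for two reactions to different treatments. That is so, but the present rule already does this within a sequence and disregards organ class.

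**Conclusion.** The concern holds. As written, two severe related reactions to one treatment in different periods never trigger the hold, and 250 of 300 subject pairs (83%) fall outside it. With 3, 4 or 5 affected subjects, the chance of no hold is 54%, 25% and 6%.

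That different periods always mean different sequences, and the pair count itself, follow from the design alone. Reading the pair count and the no-hold figures as chances assumes that reactions are unrelated to sequence. The unconditional chances also need an assumed event rate and independence between subjects. At low rates the absolute difference is small. This should be fixed because the rule fails in most of the situations it was written for and the correction is simple. It does not threaten the study's results.

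**What to change.** In the second hold criterion of Section 8.2, replace the same-sequence condition with: *in 2 subjects, counted across all treatment sequences and treatment periods*. Leave the rest of the criterion as it is.

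This keeps the threshold of 2 and every situation that triggers the hold today. Counting per treatment would be narrower, but it would lose the present trigger for two subjects in one sequence who react to different treatments.

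The cost is a protocol amendment under Section 3.6, with authority and ethics review as required, and more temporary holds: the increases are those in the last column of the table above. Sample size, sampling and analysis do not change.
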